#### **1.3.2.1 Pharmacokinetics**

Administration of tritium labeled mithramycin to monkeys showed a terminal half-life of 5 hours. The peak cerebrospinal fluid concentration: plasma ratio was 0.12 and reached after 1 ½ hours [67](#). Preliminary pharmacokinetic parameters of I-plicamycin (mithramycin) in human plasma using a radioimmunoassay were described [68](#). Three patients were studied and received mithramycin at a dose ranging from 0.85 to 1.0 mg/m^2 IV over 2 hours. Drug elimination was biphasic, with a mean elimination half-life of 10.6 hours (±1.7), and a clearance rate of 11.1± 0.4 ml/min/m^2.

Kennedy et al [52](#) administered titrated mithramycin by IV or IP routes in mice at doses closely approximating 2 mg/kg. Blood, liver, and kidney mithramycin concentrations following IP administration were similar if not higher than these observed following IV dosing. Tissue levels two hours after administration ranged from ~335 – 425 nM compared to 90 nM in blood (**Table 2**). Assuming an elimination half-life of ~10h, tissue levels most likely exceeded 50-100nM for >24h.

### **1.3.3 Clinical studies in adults**

Mithramycin underwent broad clinical evaluation in solid tumors and leukemias in the 1960's and was found to have some activity against leukemias, lymphomas and carcinomas [68-72](#); however, patient numbers and standard methods of evaluating responses were limited (**Appendix 1**). In particular, mithramycin was found to have activity against testicular cancers. In one series of 305 patients with stage III testicular cancer, 10% of patients achieved a complete response, and an additional 25% showed some evidence of tumor regression [66](#); many of these cases were

durable responses in patients with widely metastatic disease. In addition, mithramycin exhibited activity against Ewing sarcoma; two of five patients with EWFT exhibited widespread regression of metastatic disease following mithramycin treatment, one of whom had a durable complete response . This impressive response rate may be due to the ability of mithramycin to inhibit expression of EWS-FLI fusion transcript . Whereas more than 1,500 patients were treated with mithramycin, very few (~5) patients with lung cancers and no patients with esophageal carcinomas or MPM received this drug. Furthermore, only a small number of patients with breast, ovarian, or GI malignancies were treated with mithramycin. No conclusions can be drawn regarding clinical activity of mithramycin in these malignancies due to the variability of infusion schedules and timing of treatment response assessments.

Initial clinical trials suggested that 50 mcg/kg/dose, administered daily times 5 was an optimal treatment regimen . However, Spear et al  observed that 70% of 58 patients receiving this dose and schedule of mithramycin experienced significant toxicity including anorexia, nausea and vomiting. As a result, the dose of drug used in most subsequent studies was 25 mcg/kg/day on various schedules. The recommended dose in the Pfizer package insert for adults is 25-30 mcg/kg administered intravenously over 6 hours every 7-10 days of a 28 day cycle. Systemic toxicities appeared to be dose-related, tending to occur at doses above 30 mcg/kg/dose .

In general, the most frequent toxicities observed were nausea, vomiting, elevated liver function tests, infusional fever, mucositis, bleeding tendencies, thrombocytopenia, electrolyte abnormalities, proteinuria and elevated BUN/creatinine (summarized in ). Unfortunately, there was no systematic investigation of these toxicities, and it is unclear what levels of supportive care these patients received. For example, nausea and vomiting occurred quite frequently; however, in at least two reports, nausea was controlled with phenothiazines or other anti-emetics .

Hemorrhage was the most profound toxicity observed in patients receiving mithramycin. In early reports hemorrhage was attributed to thrombocytopenia, and accounted for 3 deaths in 84 patients . Subsequent studies revealed that bleeding was dose-related, occurring in 5.4% of 1150 patients treated at 30 mcg/kg/day or more . Bleeding tended to occur around day 4 of treatment, which is atypical of chemotherapy-induced thrombocytopenia. In addition, it appears that platelet counts remained >20,000/mcL in most of the patients experiencing hemorrhage, suggesting that bleeding was due to underlying clotting factor deficiencies or dysregulation of coagulation pathways. In all the cases of hemorrhage reported in the literature, it is not clear if the patients were taking any anti-coagulation medications, what type of blood product support was provided, how effective the blood product support was in that era, or what specific clinical and laboratory abnormalities were seen prior to the hemorrhage. Therefore, the frequency and severity of hemorrhage from mithramycin administered in the current era are unknown. Nevertheless, hemorrhage must be considered a rare, but serious potential toxicity of mithramycin therapy.

Additional rare but significant side effects attributable mithramycin include toxic epidermal necrolysis , and possible potentiation of anthracycline-mediated cardiotoxicity . The true incidences of these toxicities are unknown and are not discussed in the package insert from Pfizer, or the previously filed IND for mithramycin.

Mithramycin has also been used for the treatment of malignant hypercalcemia, with 45% of patients responding to a single dose of mithramycin in one study . However, the bisphosphonate, pamidronate, has replaced mithramycin in this setting. For similar reasons, mithramycin was investigated for the treatment of Paget's disease of bone and was found to have good activity in

the management of this disease. In one report, 10/10 patients with Paget's disease reported improvements in pain, and an increase in overall activity with treatment .

#### **1.3.4 Recent Experience with Mithramycin in Adult Oncology Patients at the NCI**

Twelve patients (10 males; 2 females; median age 51y; range 40-72y) with refractory thoracic malignancies (six MPMs, 2 esophageal cancers, two lung cancers, 2 synovial sarcomas) received 6h mithramycin infusions q day x 7, every 28 days. Response rates following two cycles, pharmacokinetics, and systemic toxicities (cycle 1) were evaluated. A total of 20 cycles were administered to 12 patients; all were evaluable for toxicities. No objective responses were observed in 7 patients who were evaluable for treatment responses. No myelosuppression, uncontrollable nausea or vomiting was observed. No patients experienced bleeding. The lack of these toxicities, which have been associated with mithramycin treatment  may be attributable at least in part to higher purity of the current drug relative to what had been used previously.

Eight patients experienced transient, asymptomatic dose-limiting transaminitis following 25mcg/kg/infusions. This toxicity always occurred on day 4 of the infusion. Percutaneous biopsies from three individuals revealed apoptotic hepatocellular death (**Figure 6A**). Four patients (two with MPM) had no hepatotoxicity and tolerated dose escalation to 30 mcg/kg/infusion. Peak and steady state mithramycin levels were 20 and 8nM, respectively, which were not different in patients with or without hepatotoxicity (**Figure 6B**). DMET genotyping revealed that two SNPs (rs2302387 and rs4668115) in genes encoding two related bile transporters (ABCB4 and ABCB11, respectively) were significantly associated with LFT elevations in the 12 patients treated with mithramycin (**Figure 7A** and **Figure 7B**).

promoting hepatic inflammation and LFT elevations in mice and regulates cellular accumulation of doxorubicin by a poorly-characterized non-ABC-transport mechanism^81. Mithramycin has a conjugated quinone- and semiquinone-rich structure that is similar in structure to doxorubicin, suggesting that RALBP may influence cellular accumulation of mithramycin. CYP8B1 is involved in the synthesis of cholic acid and thereby influences the composition of the bile pool. Since ABCB4 and ABCB11 are both involved in bile efflux, it is likely that CYP8B1 and these transporters are involved in hepatocellular bile accumulation. Accordingly, we suggest that the enrollment criteria of the clinical trial be amended to include the following genotypes: *RALBP* rs12680 (GG), *CYP8B1* rs6774801 (CC or CA), *ABCB4* rs2302387 (CC), and *ABCB11* rs4668115 (GG) (**Figure 8I-J**). Since *RALBP* and *CYP8B1* variant genotypes are relatively rare (variant allele frequency = 13% and 36% respectively), the present genotyping criteria should not preclude accrual of patients with thoracic malignancies.

## **2 ELIGIBILITY ASSESSMENT AND ENROLLMENT**

### **2.1 ELIGIBILITY CRITERIA**

#### **2.1.1 Inclusion Criteria**

- 2.1.1.1** Patients with measurable (per RECIST see Section **6.5.1.1**), inoperable, histologically confirmed primary lung and esophageal carcinomas, thymic neoplasms, germ cell tumors, malignant pleural mesotheliomas or chest wall sarcomas, as well as patients with gastric, colorectal or renal cancers and sarcomas metastatic to the thorax.
- 2.1.1.2** Histologic confirmation of disease in the Laboratory of Pathology, CCR, NCI, NIH.
- 2.1.1.3** Disease amenable to biopsy via percutaneous approach or other minimally invasive procedures such as thoracoscopy, bronchoscopy, laparoscopy, or GI endoscopy
- 2.1.1.4** Age  $\geq 18$ .
- 2.1.1.5** ECOG status 0-2.
- 2.1.1.6** Patients must have had or refused first-line standard chemotherapy for their inoperable malignancies.
- 2.1.1.7** Patients must have had no chemotherapy, biologic therapy, or radiation therapy for their malignancy for at least 30 days prior to treatment. Patients may have received localized radiation therapy to non-target lesions provided that the radiotherapy is completed 14 days prior to commencing therapy, and the patient has recovered from any toxicity. At least 3 half-lives must have elapsed since monoclonal antibody treatment. At least six weeks must have elapsed between mitomycin C or nitrosourea treatment.
- 2.1.1.8** Patients must have adequate organ and marrow function as defined below:
  - a) Hematologic and Coagulation Parameters:
    - i. Peripheral ANC  $\geq 1500/\text{mm}^3$
    - ii. Platelets  $\geq 100,000/\text{mm}^3$  (transfusion independent)
    - iii. Hemoglobin  $\geq 8 \text{ g/dL}$  (PRBC transfusions permitted)

- iv. PT/PTT within normal limits (patient may be eligible for trial if abnormality is deemed clinically insignificant and cleared for protocol therapy by Hematology Consult service)
  - b) Hepatic Function
    - i. Bilirubin (total) < 1.5 X upper limit of normal (ULN)
    - ii. ALT (SGPT)  $\leq$  3.0 X ULN
    - iii. Albumin > 2 g/dL
  - c) Renal Function
    - i. Creatinine within normal institutional limits or creatinine clearance  $\geq$  60 mL/min/1.73 m^2 for patients with creatinine levels above institutional normal.
    - ii. Normal ionized calcium, magnesium and phosphorus (can be on oral supplementation)
- 2.1.1.9** Cardiac Function: Left ventricular ejection fraction (EF) >40% by Echocardiogram, MUGA, or cardiac MR.
- 2.1.1.10** Ability of subject to understand, and be willing to sign informed consent
- 2.1.1.11** Female and male patients (and when relevant their partners) must be willing to practice birth control (including abstinence) during and for two months after treatment, if of childbearing potential during sexual contact with a female of childbearing potential.
- 2.1.1.12** Patients must be willing to undergo 2 tumor biopsies
- 2.1.2 Exclusion Criteria**
- 2.1.2.1** Patients with ABCB4, ABCB11, RALBP or CYP8B1 genotypes associated with mithramycin-mediated hepatotoxicity.
- 2.1.2.2** Clinically significant systemic illness (e.g. serious active infections or significant cardiac, pulmonary, hepatic or other organ dysfunction), that in the judgment of the PI would compromise the patient's ability to tolerate protocol therapy or significantly increase the risk of complications
- 2.1.2.3** Patients with cerebral metastases
- 2.1.2.4** Patients with any of the following pulmonary function abnormalities will be excluded: FEV1, < 30% predicted; DLCO, < 30% predicted (post-bronchodilator); Oxygen saturation  $\geq$  92% on room air. Arterial blood gas will be drawn if clinically indicated.
- 2.1.2.5** Patients with evidence of active bleeding, intratumoral hemorrhage or history of bleeding diatheses, unless specifically occurring as an isolated incident during reversible chemotherapy-induced thrombocytopenia
- 2.1.2.6** Patients on therapeutic anticoagulation. Note: prophylactic anticoagulation (i.e. intraluminal heparin) for venous or arterial access devices is allowed.

**2.1.2.7** Patients who are concurrently receiving or requiring any of the following agents, which may increase the risk for mithramycin related toxicities, such as hemorrhage:

- Thrombolytic agents
- Aspirin or salicylate-containing products, which may increase risk of hemorrhage
- Dextran
- Dipyridamole
- Sulfinpyrazone
- Valproic acid
- Clopidogrel

**2.1.2.8** Lactating or pregnant females (due to risk to fetus or newborn, and lack of testing for excretion in breast milk).

**2.1.2.9** Patients with history of HIV, HBV or HCV due to potentially increased risk of mithramycin toxicity in this population.

**2.1.2.10** Hypersensitivity to mithramycin

**2.1.2.11** Patients who in the opinion of the investigator may not be able to comply with the safety monitoring requirements of the study.

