## **2.2 RESEARCH ELIGIBILITY EVALUATION**

Pre-treatment blood tests should be performed within two weeks and imaging studies **within 4 weeks prior to enrollment** on the trial unless otherwise stated. The evaluations required prior to starting treatment are listed in table form in **Appendix 2: Study Calendar**.

- Complete history and physical examination including assessment of vital signs and ECOG status
- Laboratory
  - ROUTINE LABS: complete blood count, differential, LDH, SGPT (ALT), SGOT (AST), alkaline phosphatase, bilirubin (total and direct), BUN, creatinine, amylase, lipase, electrolytes, ionized calcium, magnesium, phosphorus, uric acid, albumin and thyroid panel.
    - DMET genotyping of PBMC for ABCB4/ABCB11/RALBP/ CYP8B1 SNPs (to be performed by the CLIA Molecular Diagnostics Laboratory (CLIA #21D0947274) through [name] [name]'s lab under study 06C0014). (**May be performed at any time prior to enrollment**)
  - Urinalysis.
  - Women of child-bearing potential will have a urine or serum  $\beta$ hCG pregnancy test. *Note: this test is to be done within 2 days prior to start of treatment.*

- Coagulation Studies: PT/PTT/Thrombin Time/Fibrinogen, PFA-100, VWF antigen, VWF activity, Factor VIII activity, D-dimer, Fibrin degradation products and FXIII activity, lupus anticoagulant (LA) test
- Radiographic Evaluation
  - Assessment of disease sites by appropriate radiological evaluation. This should include a CT scan of chest, abdomen and pelvis, brain MR, PET-CT, and other standard-of-care imaging specific for each patient’s malignancy.
- Cardiac Function Studies
  - Assessment of cardiac function (ejection fraction/shortening fraction) must be performed within 4 weeks of enrollment by MUGA, Echocardiogram, or cardiac MR to rule out cardiomyopathy.
  - A 12-Lead electrocardiogram (EKG) will also be performed.
- Pathologic/Tissue Evaluation
  - Histologic confirmation of tumor by the NCI Laboratory of Clinical Pathology, NIH (may be performed at any time prior to registration).

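### The Précis caps both AST and ALT at 3 x ULN for entry, but criterion 2.1.1.8(b)(ii) caps only ALT, so a patient with isolated AST elevation is ineligible by one text and eligible by the other

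*Combined protocol and SAP*

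**What the plan says.** The Précis, under Eligibility, describes sufficient liver function by three limits: total bilirubin below 1.5 x ULN, and AST and ALT at or below 3 x ULN.

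Section 2.1.1.8 introduces its laboratory list with "Patients must have adequate organ and marrow function as defined below". Its hepatic part has three lines: "Bilirubin (total) < 1.5 X upper limit of normal (ULN"), "ALT (SGPT) $\leq$ 3.0 X ULN" and "Albumin > 2 g/dL". There is no AST line.

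Other text bears on the liver before dosing:

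- Section 2.2 includes AST in the screening blood tests ("LDH, SGPT (ALT), SGOT (AST), alkaline phosphatase") without a threshold.
- Section 2.1.2.1 excludes "genotypes associated with mithramycin-mediated hepatotoxicity".
- Section 2.1.2.9 excludes "Patients with history of HIV, HBV or HCV due to potentially increased risk of mithramycin toxicity".
- Section 2.1.2.2 excludes significant "hepatic or other organ dysfunction), that in the judgment of the PI" would make treatment unsafe or poorly tolerated.
- Section 3.5.1 asks for liver elastography and serum bile acids at baseline, with no cut-off for entry. The bile acid results may come back after treatment starts.
- Section 2.3 registers patients through a separate eligibility checklist that is not part of the documents.

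**The concern.** The two statements of the entry rule disagree on one enzyme. Section 2 presents itself as the definition of acceptable organ function, so it is the text that staff would be expected to apply, and it is the more permissive of the two on AST. Two careful readers could reach opposite decisions on the same patient.

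The disagreement concerns the organ that caused the trial to be redesigned. Section 1.3.4 reports dose-limiting transaminitis in 8 of the first 12 patients, after infusions of 25 mcg/kg. Under Section 3.2, later patients start at 30 mcg/kg and, if they tolerate it, move to 50 mcg/kg. The plan treats AST as a safety signal elsewhere: the hold and reduction rules in Section 3.3 name ALT and AST together, and the Figure 8 caption reports genotype associations with elevations of both. An entry rule that checks only ALT does not match that use.

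**Working it through.** The plan states no figure to reproduce here, and no power or sample-size formula applies. The check compares the texts and then follows one patient through them.

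**Step 1. Hepatic limits side by side.**

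| Limit | Précis, Eligibility | Section 2.1.1.8(b) |
|---|---|---|
| Total bilirubin | below 1.5 x ULN | below 1.5 x ULN |
| ALT | at or below 3 x ULN | at or below 3.0 x ULN |
| AST | at or below 3 x ULN | none |
| Albumin | none | above 2 g/dL |

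Each text sets three limits and two are shared. AST appears only in the Précis and albumin only in Section 2. Both texts are current protocol text, and the numbered hepatic list in Section 2 runs without a gap or redaction.

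**Step 2. A test patient.** Take AST 4 x ULN and ALT 2.5 x ULN, with every other criterion met.

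- Précis: AST is 4, above 3, so the patient is ineligible.
- Section 2.1.1.8(b): bilirubin is met, ALT is 2.5, below 3.0, and albumin is met, so the patient is eligible.

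Whenever AST is at or below 3 x ULN, the two texts agree on transaminases. The conflict is confined to AST above 3 x ULN with ALT at or below 3 x ULN.

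**Step 3. Does anything else settle it?** Screening (2.2) measures AST without a limit. The genotype and viral hepatitis exclusions do not look at the current AST. Elastography and bile acids carry no cut-off. Section 2.1.2.2 could exclude the patient, but only by judgment. The AST rules in Section 3.3 and the chemistry schedule in 3.5.2 govern treatment and monitoring, not eligibility. The checklist in 2.3 may have an AST line or may not; the documents do not show it.

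**Step 4. Does the gap reach beyond entry?** Section 3.4 makes the next course conditional, by day 21, on the laboratory parameters of the eligibility section. If that means Section 2, re-treatment has an ALT limit and no AST limit either.

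**Step 5. Size.** A count of affected patients needs the share with AST above 3 x ULN and ALT at or below it. The documents give no such share and nothing from which to derive one.

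**The case against.** The best case against is that this is a mismatch between a summary and the body text, with little consequence. Section 2 governs, the investigator can exclude under 2.1.2.2, and the checklist actually used may already include AST. Further safeguards reduce the harm from one borderline entry: dexamethasone prophylaxis from the evening before the first dose (4.2), hospital admission for cycle 1 (3.1), and daily chemistry including AST during dosing in cycles 1 and 2 (3.5.2). Section 1.3.4 also describes the earlier transaminitis as transient and without symptoms. All of this is correct and limits the seriousness of the point. None of it supplies an AST entry limit or tells staff which text to follow.

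A second objection is that adding AST has a knock-on effect. Section 3.3 answers grade 3 ALT or AST that has not settled within 21 days with a dose reduction, whereas 3.4 requires its laboratory criteria to be met by day 21 and makes no provision for waiting. That tension already exists for ALT, and the amendment would extend it to AST. This objection stands and is dealt with in the fix.

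A reader might also infer more than the documents support:

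- **That a raised baseline AST leads to hepatotoxicity on mithramycin.** The documents link the earlier events to genotype, not to baseline AST, and those 12 patients were enrolled without genotype selection.
- **That the exposed group is everyone enrolled since amendment F, up to 57 - 12 = 45 at the accrual ceiling.** Nothing shows when the two texts came to differ or how many patients were still to be enrolled under this version.
- **That the protocol has no AST entry limit at all.** The Précis has one, and that is the source of the conflict.

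**Conclusion.** The inconsistency is confirmed. A patient with AST above 3 x ULN and ALT at or below 3 x ULN is ineligible by the Précis and eligible by Section 2, unless the principal investigator excludes them under 2.1.2.2.

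The conclusion rests on two readings: that the combined AST and ALT entry in the Précis limits each enzyme, which is the usual meaning, and that Section 2 is the operative text, as its own introduction indicates. The number of patients affected cannot be quantified from the documents. The practical effect is also unknown while the checklist is unseen.

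The two-stage design, its error rates and its stopping boundaries do not change, and there is no ground for saying that the trial's validity is at risk. This is an eligibility rule that should be corrected, because it concerns the organ with the dose-limiting toxicity and the sponsor has already stated the intended limit in the Précis.

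**What to change.** Amend 2.1.1.8(b)(ii) so that AST (SGOT) and ALT (SGPT) must each be at or below 3.0 x ULN, and make the registration checklist match.

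In the same amendment, settle the effect on Section 3.4. Either confirm that the AST limit also applies by day 21 before the next course, and state how this fits with the ALT and AST hold and reduction rules in 3.3, or state that the AST limit applies at entry only.

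If the sponsor intended ALT alone, the alternative is to remove AST from the Précis. That resolves the conflict but gives up a limit that the sponsor has itself stated.

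The cost is one line in Section 2, a matching checklist line and a clarifying sentence for 3.4. No new test is needed, since AST is already drawn at screening. An occasional patient with isolated AST elevation becomes ineligible and, if the limit also applies through 3.4, may not qualify for the next course.

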### **Eligibility:**

- Patients with measurable inoperable, histologically confirmed primary lung and esophageal carcinomas, thymic neoplasms, germ cell tumors, malignant pleural mesotheliomas or chest wall sarcomas, as well as patients with gastric, colorectal or renal cancers and sarcomas metastatic to the thorax are eligible.
- Patients with germline SNPs in ABCB4, ABCB11, RALBP or CYP8B1 that are associated with resistance to mithramycin-induced hepatotoxicity.
- Patients must have had or refused first-line standard therapy for their malignancies.
- Patients must be 18 years or older with an ECOG performance status of 0 – 2, without evidence of unstable or decompensated myocardial disease. Patients must have adequate pulmonary reserve evidenced by FEV1 and DLCO equal to or greater than 30% predicted; Oxygen saturation  $\geq 92\%$  on room air. ABG will be drawn if clinically indicated.
- Patients must have a platelet count greater than 100,000, an ANC equal to or greater than 1500 without transfusion or cytokine support, a normal PT/PTT, and adequate hepatic function as evidenced by a total bilirubin of  $<1.5 \times$  upper limits of normal (ULN) and AST/ALT  $\leq 3 \times$  ULN. Serum creatinine less than or equal to 1.6 mg/ml, or creatinine clearance greater than 70 ml/min/1.73m^2.

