### 2.3 REGISTRATION PROCEDURES

Authorized staff must register an eligible candidate with NCI Central Registration Office (CRO) within 24 hours of signing consent. A registration Eligibility Checklist from the web site (<http://home.ccr.cancer.gov/intra/eligibility/welcome.htm>) must be completed and send via encrypted email to: NCI Central Registration Office [[contact]](mailto:[contact]). After confirmation of eligibility at Central Registration Office, CRO staff will call pharmacy to advise them of the acceptance of the patient on the protocol prior to the release of any investigational agents. Verification of Registration will be forwarded electronically via e-mail to the research team. A recorder is available during non-working hours.

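### Exclusion criterion 2.1.2.4 has the oxygen saturation sign reversed: it bars patients at or above 92% on room air, the level the Précis requires for entry

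*Combined protocol and SAP*

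**What the plan says.** The eligibility summary in the Précis states the pulmonary limits as requirements: "Patients must have adequate pulmonary reserve evidenced by FEV1 and DLCO equal to or greater than 30% predicted; Oxygen saturation" is followed in the same sentence by a limit of at least 92% on room air.

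The exclusion list in Section 2.1.2 restates them as grounds for exclusion. Criterion 2.1.2.4 begins "Patients with any of the following pulmonary function abnormalities will be excluded". It gives FEV1 below 30% predicted, then "DLCO, < 30% predicted (post-bronchodilator); Oxygen saturation", and the saturation item reads in full "Oxygen saturation $\geq$ 92% on room air. Arterial blood gas will be drawn if clinically indicated".

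No other part of Section 2 states a saturation limit:

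- The inclusion list (2.1.1) has no saturation item.
- The screening list (2.2) asks for "Complete history and physical examination including assessment of vital signs and ECOG status" but gives no saturation threshold.
- The study calendar (Appendix 2) has no row for saturation or pulmonary function.

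Two provisions bear on who is admitted in practice. Criterion 2.1.2.2 lets the principal investigator exclude for clinically significant illness, including "significant cardiac, pulmonary, hepatic or other organ dysfunction". Section 2.3 requires "A registration Eligibility Checklist from the web site" to be completed, and states "After confirmation of eligibility at Central Registration Office, CRO staff will call pharmacy" before any drug is released.

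**The concern.** A requirement of at least 92% becomes, as an exclusion, below 92%. Two of the three pulmonary limits were reversed in this way and the third kept its original sign. Taken literally, the section that sets eligibility turns away adequately oxygenated patients and has no numerical bar against hypoxemic ones.

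The threshold protects patients with disease of the lung, pleura or mediastinum. They must also be willing to undergo two tumor biopsies (2.1.1.12), by routes that include percutaneous, thoracoscopic and bronchoscopic approaches (2.1.1.3).

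The wording also matters for compliance. Section 7.1.8 defines a deviation as any departure from the approved protocol, 7.2.1 requires all deviations to be reported within 7 days, and 7.4.2 has monitors check eligibility against source documents. On the literal text, enrolling a patient at 97% departs from 2.1.2.4, while enrolling one at 88% conflicts only with the Précis. Monitors and the IRB should not have to infer which text controls.

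**Working it through.** The plan has no figure to reproduce here. The check compares the set of patients that each text allows.

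**Inputs.** From the Précis: FEV1 ≥ 30, DLCO ≥ 30 and saturation S ≥ 92 are required. From 2.1.2.4: exclude if FEV1 < 30, or DLCO < 30, or S ≥ 92.

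**Rules.**

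- Précis admits: FEV1 ≥ 30 and DLCO ≥ 30 and S ≥ 92.
- 2.1.2.4 as written does not exclude: FEV1 ≥ 30 and DLCO ≥ 30 and S < 92.
- 2.1.2.4 with the sign corrected does not exclude: FEV1 ≥ 30 and DLCO ≥ 30 and S ≥ 92.

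The first two rules need S ≥ 92 and S < 92 at once, so no patient meets both. The first and third rules are identical.

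**Worked profiles.** FEV1 and DLCO are both set at 60% predicted, an illustrative value that clears those two limits, so that only saturation decides.

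| Saturation on room air | Précis | 2.1.2.4 as written | 2.1.2.4 corrected |
|---|---|---|---|
| 97% | admits | excludes | does not exclude |
| 92% | admits | excludes | does not exclude |
| 88% | does not admit | does not exclude | excludes |

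As written, 2.1.2.4 disagrees with the Précis in all three rows. Corrected, it agrees in all three.

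**Could the sign be a PDF reading error?** This is unlikely. The "less than" signs for FEV1 and DLCO in the same sentence are intact, and Section 2.1.1.8 shows both ≤ and ≥ read correctly. The saturation sign in 2.1.2.4 also matches the one in the Précis, as it would if the item had been copied across without being reversed. Suppose the source did read ≤ 92. Then 91% would be excluded, 92% excluded and 93% not excluded, against a Précis that refuses 91% and admits 92% and 93%. The texts would still differ at exactly 92%, although that would be a trivial discrepancy.

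**The case against.** The strongest reply is that this is a clerical slip with little practical effect. The lead-in speaks of abnormalities, and a saturation of 97% is not one. The neighbouring items and the Précis show the intended direction. Applied literally, the criterion would exclude every well-oxygenated candidate, so routine use would expose it.

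There are also more human checks than 2.1.2.2 and 2.3. Evaluation takes place in the Thoracic Surgery Clinic (3.1), a physician and a research nurse screen each patient before consent (10.5), and monitors unaffiliated with trial conduct verify eligibility (7.4.2).

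Most of this stands, and it limits the expected harm. It does not correct the text. Criterion 2.1.2.2 rests on judgement and gives no number. The checklist in 2.3 is not in the documents, so whether it carries the right sign is unknown. Monitors check against the protocol, which here contradicts itself.

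Two narrower points also stand. The documents state no rule of precedence between the Précis and Section 2, so treating Section 2 as controlling is a reasonable assumption, not a documented fact. And neither Section 2.2 nor Appendix 2 names oximetry, spirometry or DLCO. A saturation reading may be meant under vital signs, but the plan does not say so. The correction creates no new measurement, because both texts already depend on a room-air saturation.

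**Conclusion.** The concern holds. As written, 2.1.2.4 reverses the saturation limit and contradicts the Précis at every value of saturation. It should be fixed because it is a safety threshold in the current eligibility section, even though the intent is plain and staff would probably apply it correctly.

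The effect is confined to who may enter. The two-stage design (7 then 21 evaluable patients per cohort), its error rates and its decision rules do not change. The documents do not show how many patients, if any, were wrongly admitted or refused, and no count is claimed.

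The conclusion assumes that the sign was read correctly from the source, which the intact neighbouring signs support, and that the Précis gives the intended direction.

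**What to change.** In 2.1.2.4, change the saturation item to **oxygen saturation < 92% on room air**. The criterion then becomes the exact complement of the Précis, as the FEV1 and DLCO items already are. Confirm that the registration Eligibility Checklist used under 2.3 carries the same limit.

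The cost is one symbol and one check at the next amendment, with no change in sample size or analysis.

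A separate, optional tidy-up could go in the same amendment. The Précis renal line (creatinine up to 1.6, with the unit given as mg/ml, or clearance above 70) differs from 2.1.1.8(c) (creatinine within institutional normal limits, or clearance of at least 60). It could be aligned to 2.1.1.8(c), taking the body of the protocol as controlling. The saturation point does not depend on this.
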